I understand that the information/technology contained in this protocol is proprietary and may not be disclosed to any other party, in any form, without prior authorisation from the trial sponsor except to the extent necessary to obtain informed consent from potential trial participants.

PROTOCOL SYNOPSIS

Title:	A multicentre randomised, Double-Blind, Placebo-controlled, S tudy to evaluate the effic A cy and safety of oral IVE rmectin tablets in the prevention of COVID-19 (the SAIVE Trial)		
Protocol Number:	mdc-TTG-CT-002		
Study Phase:	II		
Sponsor:	MedinCell SA		
Coordinating Investigator:	[name]		
Study Objectives:	To assess the efficacy of ivermectin compared to placebo in the prevention of laboratory-confirmed COVID-19 infection.		
	 Secondary objectives: To assess the efficacy of ivermectin on Time to RT-PCR positive testing. To assess the efficacy of ivermectin on the occurence of severe COVID-19 symptoms. To assess the efficacy of ivermectin on Time to first COVID-19 related clinical events. To assess the efficacy of ivermectin on the rate of COVID-19 related hospitalisations. To assess the efficacy of ivermectin on the rate of COVID-19 related mortality. To assess the safety and tolerability of ivermectin given for a period of 28 days. 		
Study Design:	This is a randomised, double blind, placebo-controlled, multicen Phase II clinical trial evaluating the efficacy and safety of ivermed tablets in the prevention of COVID-19 infection. If a person tests positive for SARS-CoV-2 (index case), they obtain details of this study, in leaflet form, at the clinic or laborat where they received their positive result. The index case can the provide details of this study to their close contacts. A close contact is defined as: • Anyone who lives in the same household as another per who has tested positive for COVID-19. • Anyone who has had any of the following types of contact with someone who has tested positive for COVID-19: • Face-to-face contact including being coughed or having a face-to-face conversation within metre • Been within one metre for one minute or lon without face-to-face contact • Been within 2 metres for more than 15 minueither as a one-off contact, or cumulatively over 24-hour period • A person may also be considered a close contact they have travelled in the same vehicle or plant a person who has tested positive for COVID-19.		

	If the close contact wishes to participate in the study, they should ask the primary contact if they agree to give their informed consent by signing the form attached to the leaflet, through which primary cases agree that information related to their positive testing will be collected as evidence. Then, the contact case should get in touch with the study site and arrange for an appointment for the screening visit (within 5 days after the contact with the index case). At that appointment the contact will be screened, and they will provide the study staff with the index case's signed consent form and positive PCR test result. In addition, informed consent from the close contact must be obtained. If all eligibility criteria are met, the participant (close contact) will be randomised and a loading treatment dose will be administered. Participants will be assigned in a 1:1 ratio to receive oral daily treatment with either ivermectin or placebo. The study requires two visits to the study centre, on Day 1 and Day 28, the first and last days of treatment. In addition, there will be at least 3 remote visits that can be conducted by telephone. The treatment period lasts for 28 days in total, followed by a 28-day follow-up period, and there is a 2-day window period for visits. Therefore, total study duration for each participant is up to 58 days.			
Study Population:	Healthy volunteers between 18 and 65 years old, self-isolating after being in close contact with an individual who has had a documented exposure to COVID-19 within a maximum of 5 days prior to Screening.			
Inclusion Criteria:	 Individuals who meet all of the following criteria are eligible to participate in the study: Age between 18 and 65 years, inclusive. Body weight >45 kg. Body Mass Index >18.5. Close contact with a person who has a PCR-confirmed SARS-CoV-2 infection within 5 days before screening. Only one member in the same household will be enrolled. Participants must be able to give informed consent and comply with the study's scheduled events/visits and study assessments. SARS-CoV-2 positive index case must be able to give consent to enable collection of the documented positive PCR test. Female participants of childbearing potential must use a highly effective method of contraception for the duration of the trial. Their male partners should also use a contraception method (i.e condom) unless vasectomized. (Refer to section 4.5 Contraception Requirements). Male participants must use a contraception method (i.e condom) for the duration of the trial, unless vasectomized. Their female partners, if they are of childbearing potential, must use a highly effective method of contraception. (Refer to section 4.5 Contraception Requirements). 			

Exclusion Criteria:	Individuals who meet any of the following criteria are not eligible to			
	participate in the study:			
	1. Pregnant or breast-feeding.			
	2. Participants who have been administered COVID-19 vaccine			
	prior to the inclusion or have a planned vaccination during			
	the duration of the study.			
	3. A positive COVID-19 result (PCR or antigen test) within 8 days of screening.			
	4. Presence of typical COVID-19 symptoms (fever >38°C,			
	SpO2 below 93%, dyspnoea, difficulty breathing, chills,			
	repeated shaking with chills, ageusia, anosmia, cough,			
	myalgia, headache) in the past 48 hours prior to screening.			
	5. Presence of a known uncontrolled/unstable clinically			
	significant medical condition, considered by the investigator			
	as incompatible with study participation.			
	6. Known history of HIV, HBV and/or HCV.7. Hypersensitivity to any component of ivermectin.			
	J1 J J 1			
	8. Participants who have been administered ivermectin within 30 days prior to screening.			
	9. Participation in another interventional trial within the last 30			
	days or 5 half-lives of the IMP of the other trial, whichever			
	comes first.			
	10. Having undergone extensive bowel resection which may			
	alter ivermectin absorption.			
	11. Participants with gastrointestinal erosions and ulcers (e.g.			
	erosive esophagitis, stomach ulcers, ulcerative colitis etc.). 12. Known or clinically suspected disturbance of the blood-			
	brain-barrier (e.g., ABCB-1 [=MDR1] mutation).			
	13. History of neurotoxicity with ivermectin or other para-			
	glycoprotein (p-gp) substrates or inhibitors.			
	14. Current use of P-gp inhibitor drugs such as amiodarone,			
	azithromycin, ketoconazole, cyclosporine			
	15. Current use of monoclonal antibodies for the treatment of COVID-19.			
	16. Known drug or alcohol abuse.			
	17. Travel to endemic Loa loa regions within the past 3 months			
	prior to screening (central and western Africa).			
	18. Participants under legal guardianship or trusteeship.			
N. 1. AD. 41	100			
Number of Participants:	400 participants.			
Investigational Medicinal	Ivermectine Substipharm and a matched placebo.			
Product:	1			
Duration of Participation:	Up to 58 days (28 days of treatment and 28 days of follow-up, with			
Duranon or rarncipanon:	a 2-day window period for visits).			
Criteria for Evaluation:	Primary endpoint analysis:			

RT-PCR tests on D4, D7, D10, and D28, and at any unscheduled visits. Secondary endpoints analyses: RT-PCR tests on D4, D7, D10, and D28, and at any unscheduled visits. WHO COVID-19 and News 2 scales scoring on D1, D10, and D28, and at any unscheduled visits. COVID-19 related AE notification by participants and/or investigators throughout the study. COVID-19 related hospitalisations notified by the investigators. Duration of hospitalisation as calculated from the associated SAE notification form (date of hospital admission through to date of hospital release). COVID-19 related deaths notified by the investigators. AE notification by participants or detection by investigators. **Concomitant Medication:** Prohibited medications: The following medications are prohibited: Inhibitors of p-glycoprotien, e.g. amiodarone, azithromycin, ketoconazole, cyclosporine up to 28 days prior to randomization and throughout the study. Current pain medications such as acetylsalicylic acid or metamizol. Precautions: Some medications may have moderate or minor interactions with ivermectin. **Endpoints:** Primary endpoint: Proportion of laboratory-confirmed COVID-19 infections between baseline and Day 28. Secondary endpoints: Time to change from baseline in negative RT-PCR to positive RT-PCR. Change from baseline in the WHO-COVID 19 and NEWS-2 scores. Time to change from baseline to first COVID-19 related clinical events. Proportion of COVID-19 related hospitalisations. Proportion of COVID-19 related mortality. Safety and Tolerability of ivermectin based on treatment emergent adverse events (TEAE) and serious adverse events (SAE) according to Common

Clinical Protocol

Terminology Criteria for Adverse Events (CTCAE version 5.0). **Statistical Methods:** Sample size: Sample size was calculated to compare the proportion of participants who become positive to SARS-CoV-2 RT-PCR within 1 month after randomisation between the two groups: Placebo group and experimental group receiving ivermectin up to D28. Based on a study assessing the transmission of SARS-CoV-2 infections in households carried out in the US between April and September 2020, the proportion of randomised participants becoming infected in the placebo group is estimated to be 54% (Grijalva et al, 2020).. A difference of 20% is expected between the two groups (OR=2.28). With a power of 90% (1- β) and a significance level of 5% (α), according to the Casagrande & Pike formula the required sample size to detect such difference with a test of comparison of two proportions is equal to 138 participants per arm (Casagrande et al, 1978). A total of 396 participants (198 per arm), rounded up to 400 participants (200 per arm) is required to account for the primary analysis. This sample size also accounts for an estimated dropout rate of 30%. Primary endpoint analysis: The comparison of proportion of participants who were tested positive for SARS-CoV-2 up to D28: placebo group versus ivermectin group, will be performed using the Cochran-Mantel Haenszel (CMH) chi-squared test at the two-sided 0.05 level. Twosided 95% confidence intervals (95% CI) for the proportion differences between groups will be provided. Odds-ratio and corresponding 95% CI will also be reported. The primary endpoint will also be analysed using a logistic regression with treatment group and country as a covariate. Moreover, the analysis of the primary endpoint will be performed for the PP population.

Clinical Protocol

Safety analysis:

Safety will be pooled analyses for the Safety set from all centres and countries. Placebo and ivermectin groups will be compared.

All adverse events (AEs) will be coded according to coding dictionaries (MedDRA, applicable version) and summarised at System Organ Class (SOC) and Preferred Term (PT) levels. AEs will be classified according to period of occurrence: pre-treatment AEs, treatment-emergent AEs (TEAEs) and post-treatment AEs (PTAEs). AE reporting will focus on TEAEs and PTAEs. Incidence of TEAEs and PTEAEs will be summarised and detailed by seriousness, intensity, action taken with the study medication, other action taken and relationship to study treatment.

The number/frequency of participants with TEAEs, related TEAEs, PTAE, the number/frequency of participants with related PTAEs, SAEs and CTCAE grade 3 or more will be displayed by system organ class and preferred term according to MedDRA classification. The frequency of participants with at least one TEAE, PTAE, related PTAE, SAE and/or AE of CTAE grade 3 or more will be compared between treatment groups using a chi-squared test or a Fisher exact test.

Table 1: Schedule of Assessments

	Pre Screening D-1 or D1*	Screening & Randomisation	On-treatment period (i)				EOS (J)
		D1	D4 (±1 day)	D7 (±1 day)	D10 (±1 day)	EOT-D28** (+2 days)	D56 (±2 days)
	Remote	On-site Visit***	Remote	Remote	Remote	On-site Visit***	Remote
Study participation suitability questionnaire (a)	X						
ICF signature (b)		X					
Demographics		X					
Medical history		X					
I/C criteria		X					
Treatment dispensation		X					
Treatment administration (c)						-	
RT-PCR test (d)		X	X	X	X	X	
Antigen test (e)		X					
Serology (f)		X				X	X
NEWS-2 scale		X			X	X	
COVID-19 WHO scale		X			X	X	
Laboratory tests (g)		X				X	X
Urine pregnancy test (g)		X				X	X
Randomisation		X					
Participant diary (i)						•	
ECG		X				X	
Vital signs		X			X	X	
Adverse Events			· -				
Concomitant medication							

Clinical Protocol

- * Pre-Screening corresponds to the time frame when the first positive case is detected in the cluster within 5 days prior to screening. The study is immediately proposed to the exposed cluster members who might potentially meet the eligibility criteria (Note: only one member in the same household will be enrolled).
- ** Preferred on-site visit but can be performed remotely according to the investigator's opinion.
- *** In case of on-site visit, participants should only use private transport. Moreover, a specific room for participants has to be available and restricted to participants in order to limit their contact with patients.
- a) Participants will be questioned about their close contact to the COVID-19 index case, their interest in participating in the study, and will be given information about the study (note that full eligibility inclusion/exclusion criteria will be confirmed once the participant has signed an ICF).
- (b) ICF signature for the participant and the index case to collect information regarding his/her SARS-CoV-2 RT-PCR test results,
- (c) IMP will be administered as follows: 200 µg/kg as the loading dose admisnistered on D1at the study site, and then 100 µg/kg/day for 27 days taken by the participant at home.
- (d) PCR test to be performed on D1, D4, D7, D10 and D28: sequencing and viral load. In addition, any unscheduled test performed by the participant during the study will also be collected. Confirmed negative participants at baseline will continue RT-PCR testing, as per schedule of assessments, until they become positive or reach the planned end of study. When RT-PCR positivity is confirmed, participant will self-isolate according to local requirements.
- (e) Participants who have been tested positive at the screening with a quick antigen test will be screen failed. In addition, any unscheduled test performed by the participant during the study will also be collected,
- (f) Serology COVID-19 (antibodies levels). In addition, any unscheduled test performed by the participant during the study will also be collected).

(g) Haematology, Biochemistry, Urine pregnancy test,	for details on the parameters evaluated. Pregnancy testing must be highly sensitive, at leas
before first administration.	-

- (i) Participants will receive their diary on D1 and keep it for the duration of the treatment to record data collected between D1 and D28. They will bring it back to the site on D28.
- (J) Additional follow-up remote or on-site unscheduled visits, may be required if deemed necessary by the investigator, notably in case of emerging or prolonged adverse events. During the unscheduled visit, the investigator will evaluate the WHO COVID-19 scale and the NEWS-2 scale, in addition to any assessments deemed necessary.

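### Exclusion 9 lifts at the shorter of 30 days and 5 half-lives, so for trial drugs with a half-life above 6 days the half-life limit never operates (minor)

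*Protocol*

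**What the plan says.** Criterion 9 under Exclusion Criteria in the protocol synopsis begins "Participation in another interventional trial within the last 30" and continues "days or 5 half-lives of the IMP of the other trial, whichever", with the words 'comes first' on the next line. It therefore has a fixed limit, a limit that depends on the drug, and a rule for choosing between them. The time is counted from participation in the other trial, not from its last dose.

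Four neighbouring rules bear on the point:

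- Exclusion 2 bars anyone already given a COVID-19 vaccine, with no time limit.
- Exclusion 8 is a flat look-back for the study drug: "Participants who have been administered ivermectin within 30 days prior to screening".
- Exclusion 15 covers "Current use of monoclonal antibodies for the treatment of" COVID-19. It has no look-back and does not mention antibodies given for prevention.
- The Concomitant Medication entry prohibits P-gp inhibitors "up to 28 days prior to randomization and throughout the study".

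The supplied text has no other general washout rule for drugs from earlier trials.

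**The concern.** A limit in half-lives does most work for slowly eliminated drugs, for which a fixed 30 days may be too short. Under a rule that stops at whichever limit is reached first, it cannot do that work: for those drugs the 30 days always arrive first.

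A long-acting antibody given for prevention in another COVID-19 trial is the relevant case. It is not current use for treatment, so exclusion 15 does not apply, and exclusion 9 stops applying 30 days after participation ends. The primary endpoint is laboratory-confirmed infection between baseline and Day 28, so residual protection would remove events that the comparison relies on. SAP section 4.7.1 counts as treatment-emergent any event starting from the first intake until three days after the last, so a late effect of the other drug would be counted there.

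The per-protocol analysis would not pick these people up on this ground. Someone who satisfies exclusion 9 as written has not violated it, and SAP section 2.3 fixes no deviations in advance other than violations of the entry criteria.

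**Working it through.** **Inputs.** The 30 days, the 5 half-lives and the 'comes first' rule are from exclusion 9. The documents give no half-life for any other trial's drug, so the half-lives below are illustrative assumptions. Elimination is taken as first-order, and participation is taken to end on the day of the last dose.

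**Formulas**, with t the half-life in days:

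- Window as written: W = min(30, 5t).
- Fraction of drug left when the bar lifts: 0.5^(W/t).
- Crossover: 5t = 30, so t = 6 days.
- Benchmark after 5 half-lives: 0.5^5 = 3.1%.
- Window if the longer limit governed: max(30, 5t).

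| Assumed half-life (days) | Window as written (days) | Half-lives elapsed | Drug left | Longer limit (days) |
|---|---|---|---|---|
| 0.25 | 1.25 | 5.0 | 3.1% | 30 |
| 1 | 5 | 5.0 | 3.1% | 30 |
| 3 | 15 | 5.0 | 3.1% | 30 |
| 6 | 30 | 5.0 | 3.1% | 30 |
| 10 | 30 | 3.0 | 12.5% | 50 |
| 14 | 30 | 2.1 | 22.6% | 70 |
| 21 | 30 | 1.4 | 37.2% | 105 |
| 28 | 30 | 1.1 | 47.6% | 140 |

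For example, at 14 days: 0.5^(30/14) = 0.226. The washout shortfall lies entirely above 6 days. Below 6 days the window is short in calendar time, but 5 half-lives have passed.

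**Sensitivity to the clock.** Because the criterion counts from participation, any follow-up after the last dose lowers these residuals. One half-life of follow-up halves them: for the 14-day drug, 22.6% / 2 = 11.3%. The shortfall disappears once follow-up lasts 5t − 30 days: 70 − 30 = 40 days for a 14-day half-life and 105 − 30 = 75 days for 21 days. The tabulated figures above 6 days are therefore the worst case under the plain reading.

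**Effect on the primary contrast.** The planning figures are 54% infected on placebo and a difference of 20 percentage points. This reproduces the stated odds ratio: (0.54/0.46)/(0.34/0.66) = 2.28. If a fraction f of each arm were fully protected by an earlier trial drug, and the rest behaved as planned, the difference would be 20 × (1 − f) points. Each 1% of participants so protected costs 20 × 0.01 = 0.2 points, and partial protection costs less. The documents do not give f.

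**The case against.** Five points can be made for leaving the criterion alone.

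1. **The phrase has another reading.** In a look-back window, the limit that comes first could mean the earlier calendar date, which gives the longer window. That reading is less natural. If sites can hold both, they can apply opposite rules, so this supports clarifying the text.
2. **Current participants are already kept out.** Someone still in follow-up of another trial is still participating and is barred under either reading. This stands. It lowers the residuals, and it means a change that counted only from the last dose could loosen the rule. With a 1-day half-life, a last dose 60 days ago and follow-up continuing, the person is barred now, but a last-dose clock would set a limit of max(30, 5) = 30 days and admit them.
3. **Short half-life drugs are washed out.** A reader might infer from a bar of 1.25 or 5 days that such drugs are still on board. They are not to any extent that matters here: about 3% remains, the same benchmark used above for adequate washout.
4. **The rule is not generally looser than the plan's other washouts.** A reader might infer this from the 30 days for ivermectin and 28 days for P-gp inhibitors. Above a 6-day half-life, where the shortfall lies, exclusion 9 also gives 30 days, which equals the first and exceeds the second. Those two rules are also specific to the study drug and an interaction class.
5. **The effect does not favour an arm.** Allocation is randomised 1:1 and double-blind, so earlier exposure balances in expectation. Exclusion 2 already removes recipients of COVID-19 vaccine, including those vaccinated in a trial. This stands and limits the consequence to dilution and attribution.

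The supplied protocol text is the synopsis with the schedule of assessments, so the wording in the protocol body could not be compared.

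**Conclusion.** The point holds in a limited form, at minor severity. On its plain reading, exclusion 9 uses the shorter limit, and for any earlier trial drug with a half-life above 6 days the half-life limit has no effect. At worst, with participation ending at the last dose, about 23% (14-day half-life) to 37% (21-day) of the drug remains when the person becomes eligible. These half-lives are assumptions, and post-dose follow-up in the other trial reduces the figures. Exclusion 15 leaves past and preventive antibodies uncovered.

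The documents do not support a claim of bias towards either arm or of a material loss of power. The expected consequence is slight dilution of the infection contrast and less certain attribution of some adverse events. The number of people affected is not given and is probably small. The case for acting is that a stated rule does not do what its second limit appears meant to do, and that correcting it is cheap. That purpose is inferred from the structure of the criterion; the documents do not state it.

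**What to change.** In exclusion 9, replace the 'comes first' wording with 'whichever is longer', so that both limits must have passed. Keep participation as the basis of the criterion, and say expressly that anyone still in another interventional trial, including its follow-up, is excluded. Do not substitute a clock that runs from the last dose alone. Use the same wording wherever the criterion appears.

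The cost is a few words in one criterion and the refusal of a few recent trial participants who would now be eligible. Some of those will have taken short half-life drugs and will be refused for recent participation although their washout is complete. No analysis method or sample size changes.

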1.3 Study design

This is a randomised, double blind, parallel-group, placebo-controlled, multicentric Phase II clinical trial evaluating the efficacy and safety of ivermectin tablets in the prevention of COVID-19 infection.

If all eligibility criteria are met, the participant will be randomised, and a loading treatment dose will be administered.

Participants will be assigned in a 1:1 ratio to receive oral daily treatment with either ivermectin or placebo. Randomisation will be performed stratified by country.

The study requires two visits to the study center, on Day 1 and Day 28, the first and last days of treatment. In addition, there will be 3 remote visits (day 4, day 7 and day 10) that can be conducted by telephone.

The treatment period lasts for 28 days in total, followed by a 28-day follow-up period, and there is a 2-day window period for visits. Therefore, total study duration for each participant is up to 58 days.

Ivermectin will be supplied as 3 mg tablets and will be administered orally, under fasting conditions, as follows: 200 ug/kg as the loading dose on Day 1 and then 100 ug/kg/day for

Statistical Analysis Plan	Version 1.0		Page 7 of 25
Sponsor	MedinCell	Protocol No	mdc-TTG-CT-002

27 days. Control participants will receive placebo tablets, the number of tablets to be taken will match the number of IVM tablets taken by the active participants in the same body weight range.

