4 STATISTICAL ANALYSES

All statistical analyses will be performed using the SAS® software (Version 9.4 or later, SAS institute, North Carolina, USA).

All descriptive statistics will be given by treatment group. For baseline and basic variables, they will also be given for the entire analysis set. Screening failure data will not be analysed.

If not stated otherwise the following standard types of descriptive analyses will be presented:

- Descriptive statistics for continuous data

Statistical Analysis Plan	Version 1.0		Page 10 of 25
Sponsor	MedinCell	Protocol No	mdc-TTG-CT-002

N, mean, SD, min, lower quartile, median, upper quartile, and max will be presented. These descriptive statistics will be determined for measured values and optionally for differences to baseline.

Descriptive statistics for categorical data

Absolute frequencies and percentages will be presented. Percentage bases (denominators) will be identified in the table title or footnote (i.e. all subjects at risk, all cases). For changes from baseline, shift tables may be generated.

Inferential statistics

Unless otherwise stated, all statistical tests will be performed two-sided and at a type I error probability of α =0.05.

Unless otherwise stated, all confidence intervals (CIs) will be derived two-sided and at a confidence probability of $1-\alpha=0.95$.

Listings

All recorded data will be listed by subject sorted by treatment group. Identification variables are centre number, participant number and treatment.

Derived data will be stored in special analysis data sets and will be calculated as outlined in section 6.1.

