4.7.1 Adverse events

Adverse events will be presented by MedDRA System Organ Class (SOC) and Preferred Term (PT). Coding of verbatim terms has been performed either by Ergomed or the Sponsor and that all relevant codes are stored in the database.

Adverse events will be classified according to period of occurrence: pre-treatment AEs, treatment-emergent AEs (TEAEs) and post-treatment AEs (PTAEs).

- Pre-treatment AEs are defined as adverse events starting before the first study drug intake.
- TEAEs (i.e. during the treatment period) are defined as AEs starting from the first study drug intake until three days after the last study drug intake.
- Post-treatment AEs are defined as AEs starting four days after the treatment period (last study drug intake).

AE reporting will focus on TEAEs and PTAEs. Pre-treatment AEs will only be listed.

Frequency tables of participants experiencing at least one occasion of the event while at risk (along with the number of different occurrences of the TEAE), will be presented for the following types of adverse events:

- All TEAEs and PTAEs irrespective of the causality assessment
- TEAEs and PTAEs by CTCAE grade
- TEAEs and PTAEs by action taken with the study medication
- Related TEAEs and PTAEs
- Serious TEAEs and PTAEs (SAEs)
- Related serious TEAEs and PTAEs
- Fatal TEAEs or PTAEs

[figure not shown]
Statistical Analysis Plan	Version 1.0		Page 17 of 25
Sponsor	MedinCell	Protocol No	mdc-TTG-CT-002

Participants will only be counted once within a PT or SOC.

SOC terms will be presented according to the Internationally Agreed Sorting Order (MedDRA).

Comparison between the treatment groups on the number of participants with TEAEs/PTAEs will be performed by means of a Fisher's exact test.

Detailed listings of all fatal and other serious events will be provided (for section 14.3.2). Narratives will not be included in section 14.3.3 but will be provided by medical writing in section 12.3.2 of the CSR. All adverse events (i.e. TEAEs as well as non-treatment emergent events) will be listed in section 16.2 of the CSR. However, only TEAEs and PTAEs will be summarized in the tables.

Statistical Analysis Plan	Version 1.0		Page 18 of 25
Sponsor	MedinCell	Protocol No	mdc-TTG-CT-002

Statistical Analysis Plan	Version 1.0		Page 19 of 25
Sponsor	MedinCell	Protocol No	mdc-TTG-CT-002

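### Adverse-event tests ignore country, the randomisation stratum: with several countries and differing AE rates this can cost power to detect an excess of common events (minor)

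*Protocol*

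**What the plan says.** - **Randomisation.** SAP 1.3: "Randomisation will be performed stratified by country", with 1:1 allocation.
- **Efficacy proportions.** SAP 4.6.1 (primary) and 4.6.2 (secondary) use the CMH test with country as stratification factor and report odds ratio, relative risk and risk difference with 95% CI. Both sections fall back to an unstratified chi-squared or Fisher test if the study ran in a single country.
- **Safety, protocol.** Synopsis, Statistical Methods, Safety analysis: "Safety will be pooled analyses for the Safety set from all centres and countries". The frequencies of participants with at least one event in the listed categories (TEAE, PTAE, related PTAE, SAE, grade 3 or more) "will be compared between treatment groups using a chi-squared test or a Fisher exact test".
- **Safety, SAP.** Section 4.7.1: "Comparison between the treatment groups on the number of participants with TEAEs/PTAEs will be performed by means of a Fisher's exact test". Country is not mentioned.
- **Level.** SAP 4 sets the general rule that, unless otherwise stated, "all statistical tests will be performed two-sided and at a type I error probability of" 0.05. This covers the AE tests.

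The text reviewed gives no number of countries, no country shares, no expected AE rates, and no power target or decision rule for safety.

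**The concern.** The plan randomises within country and carries country into its tests of efficacy proportions, but drops it from the AE tests without giving a reason. Stratified randomisation balances country between the arms. A pooled test still counts between-country variation in its variance, so when AE rates differ by country its variance is too large and its true level falls below the nominal one.

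For a harm comparison that is the unhelpful direction, because a real excess on ivermectin becomes more likely to be reported as not significant. Safety and tolerability is a stated objective. AEs also depend on notification by participants or detection by investigators, so reporting rates could plausibly differ between countries, although the documents do not show that they do.

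There is also a small inconsistency. COVID-19 related hospitalisation falls under CMH by country as a secondary endpoint. The same hospitalisations, recorded as SAEs, fall under an unstratified test.

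**Working it through.** **1. The plan's own figure.** The only sample-size calculation is for the primary endpoint: 54% against 34%, two-sided 5%, 90% power, Casagrande & Pike.

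- A = [1.960·√(2·0.44·0.56) + 1.2816·√(0.54·0.46 + 0.34·0.66)]² = (1.376 + 0.881)² ≈ 5.09
- n = A·[1 + √(1 + 4·0.20/A)]² / (4·0.20²) = 137.2, so 138 per arm
- 138/0.70 = 197.1, so 198 per arm, rounded in the plan to 200
- OR = (0.54/0.46)/(0.34/0.66) = 2.28

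All of these reproduce. There is no corresponding figure for the AE tests, so the rest rests on assumptions.

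**2. Assumptions (not in the documents).** 200 per arm in the safety set, equal country shares, exact 1:1 balance within country, a common AE odds ratio of 1.6, and the placebo AE rates shown below.

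**3. Effect of pooling on the level.** Let R be the mean within-country p(1−p) divided by p̄(1−p̄), where p̄ is the overall rate. The pooled chi-squared test then has approximate level 2·[1 − Φ(1.96/√R)].

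- Equal rates, or one country: R = 1, level 5.0%
- 25%/40%: R = 0.21375/0.21938 = 0.974, level 4.7%
- 20%/50%: R = 0.205/0.2275 = 0.901, level 3.9%
- 10%/30%/60%: R = 0.180/0.2222 = 0.81, level 2.9%
- 1%/3% (SAE-type): R = 0.0195/0.0196 = 0.995, level 4.9%, so pooling has almost no effect

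R cannot exceed 1, so with balanced arms pooling can only make the test conservative.

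**4. Power, separating pooling from Fisher.** Simulated power (%) at odds ratio 1.6:

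| Placebo AE rates by country | Pooled Fisher | Pooled chi-squared | CMH by country | Lost to Fisher | Lost to pooling |
|---|---|---|---|---|---|
| 30%/30% | 57 | 61 | 61 | 4 | 0 |
| 25%/40% | 56 | 60 | 61 | 4 | 1 |
| 20%/50% | 48 | 53 | 58 | 5 | 5 |
| 10%/30%/60% | 39 | 44 | 53 | 5 | 9 |

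The fifth column is chi-squared minus Fisher; the last is CMH minus chi-squared. Repeat runs move single entries by about one point, so the mild case is best read as 1 to 2 points. For rare events (1%/3%), pooled chi-squared and CMH coincide at about 10% power.

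**5. Sensitivity at odds ratio 1.8.** Pooled Fisher / pooled chi-squared / CMH, power in %:

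- 20%/40%: 74/77/78
- 10%/50%: 57/61/70
- 10%/70%: 34/39/62
- 1%/3%: 8/15/15

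The pattern is the same. Pooling matters only for common events with a wide spread between countries. Fisher's loss is present throughout, and its level is 4.0% even when both countries have a 30% rate.

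**The case against.** Several points against the concern are sound.

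- **It is conditional.** A reader might infer that the safety test does run below 5% and does lose power because it is pooled. The documents do not support that. It needs more than one country and differing AE rates; neither is given, and SAP 4.6.1 and 4.6.2 expressly allow for a single-country study.
- **Two causes are easily mixed.** A reader might charge the whole gap between pooled Fisher and CMH to pooling. In the mild case most of it comes from the discreteness of Fisher's test. The protocol also permits chi-squared; the SAP narrows the choice to Fisher.
- **No bias.** With 1:1 allocation within country, pooling does not distort the comparison of overall AE proportions.
- **No gain for rare events.** Stratifying adds essentially nothing for SAEs.
- **No decision hangs on the p-value.** Safety has no power target, margin or decision rule. AEs will be read mainly from tables by organ class, grade, relatedness and seriousness, and from listings.
- **Partly covered.** COVID-19 related hospitalisation and mortality already fall under country-stratified CMH in SAP 4.6.2.

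These points limit the size and seriousness of the concern. They do not explain why country is used for efficacy proportions and omitted for AEs, and none of them identifies a material cost in using it.

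**Conclusion.** The mismatch is in the text: country is a randomisation stratum and an efficacy stratum, but the AE tests do not use it. The consequence is possible loss of sensitivity, not invalidity. Under the assumptions above, pooling costs between nothing and about 9 points of power at odds ratio 1.6. The upper end needs rates as far apart as 10%, 30% and 60%, which nothing in the documents establishes. The SAP's choice of Fisher costs a further 4 to 5 points whether or not countries differ.

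This is a minor point. It is worth acting on because the planned test errs in the direction that hides harm and the remedy follows a rule already in the SAP.

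**What to change.** Amend SAP 4.7.1 and align the protocol's safety text:

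- Compare the frequent categories (any TEAE, any PTAE) by CMH stratified by country, with the risk difference and 95% CI, as SAP 4.6.2 does for efficacy proportions.
- For sparse categories, use the exact conditional test stratified by country. Name in advance which categories take which test, so that the choice does not depend on the data. The exact test stays somewhat conservative: at 20%/50% and odds ratio 1.6 its power was about 54%, between pooled Fisher and CMH.
- Keep the pooled AE tables for display.
- If only one country enrols, use the unstratified chi-squared or Fisher test, as SAP 4.6.1 already provides for efficacy.

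The cost is a few sentences and one stratum variable in the SAS programs, with no new data. SAP 2.1 already allows for an amendment before database lock and unblinding.
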